6.2. Primary Efficacy Endpoint

The primary efficacy endpoint is the proportion of subjects who achieve ACR20 response at Week 12.

6.2.1. Definition of the Primary Efficacy Endpoint

6.2.1.1. ACR20

A subject achieves ACR20 response when this subject has

- $\geq 20\%$ improvement from baseline in TJC68, AND
- $\geq 20\%$ improvement from baseline in SJC66, AND

- $\geq 20\%$ improvement from baseline in at least 3 of the following 5 items:
 - PGADA (0 – 100 visual analog scale (VAS))
 - PhGADA (0 – 100 VAS)
 - HAQ-DI's pain assessment (0 – 100 VAS)
 - Patient's assessment of physical function as measured by HAQ-DI score
 - hsCRP

Percent improvement from baseline at a postbaseline visit is calculated as follows for all 7 components mentioned above:

$$\% \text{improvement} = \frac{\text{baseline value} - \text{postbaseline value}}{\text{baseline value}} \times 100$$

If the baseline value is 0 then the percent improvement from baseline is set to missing. In the case that some ACR20 components are missing, the ACR20 assessment will be based on the nonmissing components. If nonmissing components are not sufficient to determine ACR20 response, then the ACR20 response will be considered as missing.

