- Step 2: Within each analysis visit window, select the component-level data based on the rules for selecting efficacy data as above
- Step 3: Calculate the composite endpoint based on the selected component-level data in Step 2.

Missing Data Consideration

Unless specified otherwise, below are the consideration for the missing data that will be used throughout the efficacy analyses:

Observed case (OC): Missing values remain missing. For the categorical composite endpoints, in the case that some components are missing, the composite endpoint assessment will be derived based on the nonmissing components. If nonmissing components are not sufficient to determine final composite endpoint, then the composite endpoint will be set as missing. For continuous composite endpoints, if any components are missing, the composite endpoints will be set as missing.

If a subject only has baseline measurements, OC analyses will not include this subject.

For subjects who were re-randomized, the baseline value for the LTE phase will be the last nonmissing measurement obtained on or prior to the first dose date of filgotinib in the LTE. The change from baseline at analyses visits during LTE phase will be assessed from the re-randomized baseline of the LTE phase. The evaluation of response at analysis visits during LTE phase will be assessed from the re-randomized baseline of the LTE phase.

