6.2.2. Primary Analysis of the Primary Efficacy Endpoint

To test for superiority of filgotinib 200 mg or filgotinib 100 mg group versus placebo control group in proportion of subjects who achieve ACR20 at Week 12, a logistic regression analysis with treatment groups and stratification factors in the model will be used. The model will include all treatment groups. Missing data on the ACR20 response rate at Week 12 will be imputed using multiple imputation (MI) assuming missing at random (MAR):

- The MI procedure replaces each missing binary ACR20 value with a set of plausible values that represent the uncertainty about the right value to impute. Twenty imputed datasets will be generated with starting seed 12345. These multiple imputed data sets are then analyzed by using the same method for the primary analysis for complete data as specified above. The results from each set of imputed data sets will then be combined using Rubin’s rule {[Rubin 1987](#)}. The stratification factors and treatment groups will be included in the imputation model as covariates and all available data at post-baseline visits up to Week 16 visit will be included in the longitudinal model.

The p-value from the logistic regression model with MI for testing the superiority of filgotinib 200 mg or filgotinib 100 mg as compared to placebo will be provided. The 2-sided 95% confidence interval (CI) of the ACR20 response rate at Week 12 based on MI method will be provided for each treatment group. In addition, treatment difference in ACR20 response rate at Week 12 between each filgotinib dose group and placebo group along with its 95% CI calculated based on MI method will be provided.

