6.3.1. Definition of Key Secondary Efficacy Endpoints

6.3.1.1. ACR50

ACR50 is similarly defined as ACR20 (see Section 6.2.1), except that the improvement threshold from Baseline is 50%.

6.3.1.2. 36-Item Short-form Health Survey (SF36v2)

The SF-36 Version 2 is a 36-item, self-reported, generic, comprehensive, and health-related quality of life questionnaire that yields an 8 health domains (physical functioning, role-physical, bodily pain, general health, vitality, social functioning, role-emotional, and mental health). Each domain is scored by summing the individual items and transforming the scores into a 0 to 100 scale with higher scores indicating better health status or functioning. In addition, 2 summary scores, the physical component summary (PCS) score and the mental component summary (MCS) score will be evaluated based on the 8 SF-36 domains.

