6.3.2. Analysis Methods for Key Secondary Efficacy Endpoints

For the superiority test of filgotinib 200 mg or filgotinib 100 mg group versus placebo control group in binary key secondary endpoints such as the ACR50 response rate at Week 12, the PASI75 response rate at Week 16 in subjects with psoriasis covering $\geq 3\%$ of the BSA at Baseline and the MDA response rate at Week 16, the observed response rate and 2-sided 95% CI based on normal approximation with continuity correction will be provided by visit. Non-stratified response rate difference along with its 95% CI calculated based on the normal approximation with continuity correction will be provided. Appendix 4 provides sample SAS models statements for constructing the confidence interval for the proportion. In addition, the p-value based on the logistic regression model same as the one used in section 6.2.2 with observed cases for testing the superiority of filgotinib 200 mg or filgotinib 100 mg as compared to placebo will be provided as well. In case of limited data leading to improper use of logistic model, the p-value will not be provided.

For non-inferiority test of filgotinib 200 mg or filgotinib 100 mg group versus adalimumab group in the ACR20 response rate at Week 12, the approach proposed by {Liu 2014} will be used to demonstrate that each filgotinib dose preserves more than 50% of the effect of adalimumab on the response rate of ACR20 at Week 12. Let π_T , π_C and π_P denote the true response rates of ACR20 for filgotinib, adalimumab and placebo, respectively, at Week 12, with corresponding variances σ_T^2 , σ_C^2 and σ_P^2 . The non-inferiority hypotheses are

$$H_{0,NI} : \frac{\pi_T - \pi_P}{\pi_C - \pi_P} \leq 0.5$$

vs

$$H_{1,NI} : \frac{\pi_T - \pi_P}{\pi_C - \pi_P} > 0.5$$

According to {Liu 2014}, the test statistics for non-inferiority (filgotinib preserves more than 50% of the effect of adalimumab) is

$$Z_{NI} = \frac{\hat{\pi}_T - 0.5\hat{\pi}_C - (1 - 0.5)\hat{\pi}_P}{\sqrt{\hat{\sigma}_T^2 + 0.5^2\hat{\sigma}_C^2 + (1 - 0.5)^2\hat{\sigma}_P^2}}$$

Note that the “hat” (^) denotes the estimated values of each parameter at Week 12. Missing data will be imputed using multiple imputation (MI) assuming that missing data are missing at random (MAR), which will follow the same method as described for the primary endpoint.

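### An ACR item that starts at 0 is set to missing, so some certain ACR20 non-responders become missing and are then imputed or dropped

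*SAP*

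**What the plan says.** SAP 6.2.1.1 defines an ACR20 responder as a subject with at least 20% improvement in TJC68, in SJC66, and "improvement from baseline in at least 3 of the following 5 items": PGADA, PhGADA, HAQ-DI pain, HAQ-DI score and hsCRP. Percent improvement is the fall from baseline divided by baseline. For a zero denominator the rule is "If the baseline value is 0 then the percent improvement from baseline is set to missing". The composite is then judged on what remains: "If nonmissing components are not sufficient to determine ACR20 response, then the ACR20 response will be considered as missing". SAP 6.1 has the same rule for observed-case analyses: "If nonmissing components are not sufficient to determine final composite endpoint, then the composite endpoint will be set as missing".

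What happens next depends on the endpoint:

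- **ACR20 at Week 12 (SAP 6.2.2).** Missing values are multiply imputed under MAR. The model uses treatment, stratification factors and post-baseline data up to Week 16. The non-inferiority test in SAP 6.3.2 uses the same imputation.
- **ACR50 at Week 12 (SAP 6.3.1.1 and 6.3.2).** The definition is taken over from ACR20 at the 50% threshold. The analysis takes "the p-value based on the logistic regression model same as the one used in section 6.2.2 with observed cases".
- **ACR20, ACR50 and ACR70 by visit (SAP 6.4.2).** Observed cases.

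SAP 6.5 states that no sensitivity analyses will be done.

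**The concern.** A percentage change from 0 is undefined, but the clinical fact is not. HAQ-DI runs from 0 to 3 and the VAS items from 0 to 100, so a subject who starts at 0 cannot improve on that item. It is known not to count toward the 3 of 5. The SAP treats this known failure as unknown.

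Take a subject with HAQ-DI 0 at baseline, both joint counts improved and exactly 2 of the other 4 items improved. At most 2 of 5 items can qualify, so this is a non-responder with complete data. Under the SAP the fifth item is open, the composite is undetermined, and ACR20 becomes missing.

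This missingness depends on the outcome itself, because only non-responders enter the group. As described, the imputation model works on the binary ACR20 value and does not know that response was impossible. A fully observed non-responder can therefore receive a positive chance of response in the primary endpoint.

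**Working it through.** **The plan's own figure.** The plan gives no number on this point. Its design figure for ACR20 at Week 12 is 90% power for non-inferiority (SAP 1.3: rates 0.60, 0.52 and 0.386; n = 244, 122 and 244; two-sided 0.025). With the SAP 6.3.2 statistic:

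- Numerator: 0.60 − 0.5 × 0.52 − 0.5 × 0.386 = 0.147
- Standard error: √(0.60 × 0.40/244 + 0.25 × 0.52 × 0.48/122 + 0.25 × 0.386 × 0.614/244) = 0.0417
- Z = 3.526; power = Φ(3.526 − 2.241) = 0.901

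The stated 90% reproduces, and this point does not change it.

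**Which items can be 0 at baseline?**

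- Joint counts: no. Protocol 4.2 requires at least 3 swollen and 3 tender joints on Day 1.
- hsCRP: not expected. SAP 3.6 gives values below the limit of quantitation a non-zero number.
- HAQ-DI and the three VAS items: yes. Protocol 4.2 and 4.3 set no minimum. HAQ-DI 0 is the realistic case.

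**Which patterns change status?** All patterns were enumerated with both joint counts improved, *m* items at baseline 0 and *k* of the other 5 − *m* items improved. The true status is responder if k ≥ 3. Under the SAP the status is missing if k < 3 and k + m ≥ 3.

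| Zero-baseline items | Patterns | Non-responder under both | Non-responder, but missing under SAP | Responder under both |
|---|---|---|---|---|
| 0 | 32 | 16 | 0 | 16 |
| 1 | 16 | 5 | 6 (k = 2) | 5 |
| 2 | 8 | 1 | 6 (k = 1 or 2) | 1 |

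No true responder becomes missing. Counting a zero-baseline item as not improved restores all 6 patterns in each of the last two rows and changes no responder.

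**How many subjects?** The inputs here are assumptions. Let J be the probability that both joint counts improve, p the improvement probability of each other item (taken as independent), and q the share of subjects with one zero-baseline item. Then P(affected | one zero item) = J × 6 × p² × (1 − p)².

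- Lowest (J = 0.4, p = 0.7): 0.4 × 6 × 0.49 × 0.09 = 0.106
- Highest (J = 0.7, p = 0.5): 0.7 × 6 × 0.25 × 0.25 = 0.262

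| q | Share of all subjects | Of 67 enrolled |
|---|---|---|
| 2% | 0.2% to 0.5% | 0.1 to 0.4 |
| 5% | 0.5% to 1.3% | 0.4 to 0.9 |
| 10% | 1.1% to 2.6% | 0.7 to 1.8 |

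Items are likely to be correlated, which lowers the probability. Simulations with item rates of 50% to 72% and correlation 0.4 or 0.6 gave 0.05 to 0.11, depending on the joint-count rates assumed. With q from 5% to 15%, that is 67 × 0.05 × 0.05 = 0.2 to 67 × 0.15 × 0.11 = 1.1 subjects.

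**Effect on a rate.** If a fraction u of an arm with true rate r is affected, the observed-case rate is r/(1 − u). Imputation at the arm's observed rate gives the same: r + u × r/(1 − u) = r/(1 − u). At u = 1% and 2%, 0.600 becomes 0.606 and 0.612, and 0.386 becomes 0.390 and 0.394. In an arm of about 19 (67 × 2/7), losing one such non-responder moves 11/19 = 57.9% to 11/18 = 61.1%.

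**The case against.** The strongest objection concerns the reading. The SAP judges ACR20 on the nonmissing components and makes it missing only if these do not settle the matter. A programmer might hold that 2 improved items already fail a 3-of-5 rule, and the problem would not arise. But the SAP expressly orders the item to be missing, and an item that is missing could still be the third. The plain reading leaves the composite undetermined. If two programmers could differ on the primary endpoint, the text needs the sentence anyway.

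The objections on scope and size have more force:

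- Only the pattern above is affected. Most subjects with a zero-baseline item keep the right status.
- The upward direction holds within an arm. The primary summary is a difference between arms, and its direction depends on how the affected share differs between them. The imputation also uses other visits, so observed non-response there may lower the imputed chance.
- The size rests on assumptions throughout. Taking 67 as the base is generous, since some subjects may have no Week 12 assessment.
- The trial stopped at 67 of 854 subjects, p-values are nominal (SAP 3.4), and the planned by-subject listings of endpoints and components (SAP 6.4.2) would let a reader find an affected case.

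All of this limits the consequence. None of it makes the rule give the right status.

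**Conclusion.** The concern holds. As written, the baseline-0 rule gives a wrong status to a defined group of non-responders: both joint counts improved, fewer than 3 items improved, and enough zero-baseline items to reach 3 if they were counted. They are then imputed for ACR20 at Week 12 and dropped from the observed-case ACR analyses. Each arm's response rate can only be pushed up.

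The size is small, probably 0 to 2 of the 67 subjects, and rests on an assumed share of zero baselines that the documents do not supply. One subject can still move the rate in an arm of about 19 by some 3 percentage points. Sample size and power are unaffected. This is a worthwhile correction to an endpoint definition and does not threaten the trial's conclusions.

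**What to change.** Replace the baseline-0 sentence in SAP 6.2.1.1 with a rule that, for ACR20, ACR50 and ACR70, an item with a baseline of 0 is counted as not improved, and that only items not measured at baseline or at the visit are missing. ACR50 and ACR70 inherit the change through SAP 6.3.1.1 and 6.4.1.8.

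The cost is one sentence and a small change to the ACR derivation. It creates no new missing values and changes no responder. Because the SAP is a signed version 1.0, the change should be recorded in the CSR, as SAP 1 already provides, with the number of subjects whose status it alters.

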6.2.1.2. ACR Components

6.2.1.2.1. Tender/Swollen Joint Counts (TJC/SJC)

TJC68 and SJC66 will be collected during the course of the study. The assessment for each joint will be from the following selections: Normal, Tender, Swollen, Tender and Swollen or Not able to evaluate.

Individual joint with missing/non-evaluable assessment will not be imputed. If at least half of the joints are assessed and evaluable at a given visit, the prorated tender and swollen joint counts will be calculated using the following formula:

$$\text{TJC68} = \frac{\text{Total number of tender joints}}{68 - (\text{Number of missing/nonevaluable joints out of 68 joints})} \times 68$$

$$\text{SJC66} = \frac{\text{Total number of swollen joints}}{66 - (\text{Number of missing/nonevaluable joints out of 66 joints})} \times 66$$

If less than half of joints are assessed and evaluable at a given visit, joint counts are treated as missing for that visit.

A more abbreviated assessment considering 28 joints as listed in Table 6-1 for both tenderness and swelling will also be conducted (as part of the TJC68 and SJC66 assessment), denoted as TJC28 and SJC28, respectively.

Table 6-1. Composition of the 28 Joints

Joints	Number
Shoulder Joints (Left and Right)	2
Elbow Joints (Left and Right)	2
Wrist Joints (Left and Right)	2
Metacarpophalangeal Joints I-V (Left and Right) – hands only	10
Proximal Interphalangeal Joints I-V (Left and Right) – hands only	10
Knee Joints (Left and Right)	2

If there exist non-evaluable or missing joints among the 28 joints, similar prorated tender and swollen joint counts will be calculated as follows:

$$TJC28 = \frac{\text{Total number of tender joints}}{28 - (\text{Number of missing/nonevaluable joints out of 28 joints})} \times 28$$

$$SJC28 = \frac{\text{Total number of swollen joints}}{28 - (\text{Number of missing/nonevaluable joints out of 28 joints})} \times 28$$

If less than half of the 28 joints are assessed and evaluable at a given visit, TJC28 and SJC28 are treated as missing for that visit.

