4.3. Exclusion Criteria

Subjects who meet *any* of the following exclusion criteria are not to be enrolled in this study.

- 1) Known hypersensitivity to the study drug, the metabolites, or formulation excipients
- 2) Prior PsA or psoriasis treatment with a bioDMARD
- 3) Prior exposure to a JAK inhibitor >2 doses

- 4) Corticosteroid use as follows:
 - a) Intra-articular corticosteroids ≤ 8 weeks of Day 1
 - b) Parenteral corticosteroids ≤ 2 weeks of Day 1
- 5) Use of any of the following treatments ≤ 4 weeks of Day 1:
 - a) Intra-articular injection of hyaluronate therapies
 - b) Oral retinoids (including tazarotene)
 - c) Phototherapy (UVA or UVB) with or without psoralens or self-treatment with sunbathing or tanning beds
 - d) Potent P-glycoprotein (P-gp) inducers (e.g. carbamazepine, clotrimazole, dexamethasone, phenothiazine, phenytoin, retinoic acid, rifampin, St. John's wort and venlafaxine)
 - e) Oral or injectable gold
 - f) D-penicillamine
 - g) Cytotoxic agents including chlorambucil, cyclophosphamide, nitrogen mustard, or other alkylating agents
- 6) Any moderately to severely active musculoskeletal or skin disorder other than PsA or plaque psoriasis that would interfere with assessment of study parameters, as per judgment of investigator

NOTE: Prior history of reactive arthritis or axial spondyloarthritis is permitted if there is documentation of change in diagnosis to PsA or an additional diagnosis of PsA
- 7) Any history of an inflammatory arthropathy with onset before age 16 years old
- 8) Active autoimmune disease that would interfere with assessment of study parameters or increase risk to the subject by participating in the study, (e.g. uveitis, inflammatory bowel disease, uncontrolled thyroiditis, systemic vasculitis, transverse myelitis), per judgement of investigator
- 9) Presence of any extra-articular manifestations typically associated with RA, such as rheumatoid nodules, rheumatoid lung, or other signs / symptoms, as per judgement of investigator
- 10) Have undergone surgical treatments for PsA, including synovectomy or arthroplasty in >4 joints and / or ≤ 12 weeks prior to Day 1
- 11) History of major surgery (requiring regional block or general anesthesia) ≤ 3 months prior to Screening or planned major surgery during the study

- 12) Administration of a live / attenuated vaccine ≤ 30 days prior to Day 1, or planned during the study

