Appendix 24. SJC66 / TJC68: Swollen and Tender Joint Count

An overview of the (66 / 68) joints to be assessed bilaterally are provided below:

- Temporomandibular
- Sternoclavicular
- Acromioclavicular
- Shoulder
- Elbow
- Wrist
- Metacarpophalangeal: first, second, third, fourth, fifth
- Proximal interphalangeal: first, second, third, fourth, fifth
- Distal interphalangeal: second, third, fourth, fifth
- Hip¹
- Knee
- Ankle
- Tarsus
- Metatarsophalangeal: first, second, third, fourth, fifth
- Proximal interphalangeal (toe) : first, second, third, fourth, fifth

Replaced / missing (or otherwise not assessable) joints should be documented at Day 1 and omitted from further evaluation during the study.

¹ Assessed for tenderness only

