6.3.1.5. Minimal Disease Activity (MDA)

MDA is a measure to indicate disease remission, and is based on a composite score of 7 domains.

A subject will be classified as having achieved MDA when at least 5 out of 7 of the following criteria are met.

- TJC68 ≤ 1,
- SJC66 ≤ 1,

- $PASI \leq 1$ for subjects with a Baseline psoriasis covering at least 3% of the BSA (or for subjects with a Baseline psoriasis covering $BSA < 3\%$, this criterion is considered met),
- Patent’s Global Assessment of PsA pain intensity (PGAPI) score ≤ 15 (0 – 100 VAS),
- $PGADA \leq 20$ (0 – 100 VAS),
- $HAQ-DI \leq 0.5$,
- Leeds Enthesitis Index ≤ 1 for subjects with enthesitis at Baseline (or for subjects without enthesitis at Baseline, this criterion is considered met).

In the case that some of the MDA components are missing, the MDA assessment will be based on the nonmissing components. If nonmissing components are not sufficient to determine the MDA response, then the MDA response will be considered as missing.

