6.4.1.3. Very Low Disease Activity (VLDA)

VLDA is defined based on the same 7 criteria as in MDA. A subject will be classified as having achieved VLDA when all 7 out of 7 of the criteria are met. In the case that some of the VLDA components are missing, the VLDA assessment will be based on the nonmissing components. If nonmissing components are not sufficient to determine the VLDA response, then the VLDA response will be considered as missing.

6.4.1.4. Disease Activity Index for Psoriatic Arthritis (DAPSA), DAPSA LDA, DAPSA remission and Time to Achieve DAPSA LDA

$DAPSA = TJC68 + SJC66 + PGADA (0 - 100 \text{ VAS})/10 + PGAPI (0 - 100 \text{ VAS})/10 + CRP$ (mg/dL).

where

PGADA = Patient's Global Assessment of Disease Activity (0 – 100 VAS);

PGAPI = Patient's Global Assessment of PsA Pain Intensity (0 – 100 VAS);

CRP is in unit of mg/dL.

If any of the components is missing, then DAPSA remains missing.

The derived DAPSA binary parameters include:

- DAPSA remission: $DAPSA \leq 4$,
- DAPSA LDA: $DAPSA \leq 14$.

The time to achieve DAPSA LDA is defined as:

Date of first (DAPSA \leq 14) – First dose date of any study drug + 1

For each subject included in the analysis, all available measurement for DAPSA will be considered for the time to achieve DAPSA LDA based on the treatment policy estimand.

The time to achieve DAPSA LDA can be derived for the subject in each treatment group based on the data during Main study phase. If the DAPSA LDA is not achieved during Main study phase, the time to achieve DAPSA LDA will be censored at the last nonmissing DAPSA assessment date during Main study phase. If the component scores of DAPSA are at different dates for a visit, the latest date will be used for the derivation of time to achieve DAPSA LDA.

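### Unrounded prorated joint counts are tested against ≤ 1, so one active joint plus one unevaluable joint in the same count fails the MDA/VLDA joint criterion

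*SAP*

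**What the plan says.** **Joint counts (SAP 6.2.1.2.1).** "Individual joint with missing/non-evaluable assessment will not be imputed". Instead, the count is scaled up: "If at least half of the joints are assessed and evaluable at a given visit", then "the prorated tender and swollen joint counts will be calculated using the following formula". The formula is active joints ÷ (N − missing or unevaluable joints) × N, with N = 68 for tenderness and 66 for swelling. No rounding is mentioned, and no separate observed count is defined. The assessor's response options include one for a joint that cannot be evaluated.

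**Use of the counts.** SAP 6.3.1.5 lists TJC68 ≤ 1 and SJC66 ≤ 1 among the seven MDA criteria. A subject has MDA when "at least 5 out of 7 of the following criteria are met". SAP 6.4.1.3 adds that "VLDA is defined based on the same 7 criteria as in MDA" and requires all seven.

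**Where unevaluable joints come from.** Protocol Appendix 24 states: "Replaced / missing (or otherwise not assessable) joints should be documented at Day 1 and omitted from further evaluation during the study". Exclusion criterion 10 in Protocol 4.3 covers surgical treatment for PsA, "including synovectomy or arthroplasty in >4 joints and / or ≤ 12 weeks prior to Day 1". Subjects with one to four older replacements can therefore enrol.

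**The concern.** Proration turns a whole-number count into a fraction, and the MDA and VLDA criteria then compare that fraction with a whole-number limit. At the limit, any upward scaling, however slight, changes the result. A subject with one active joint and one joint replaced years ago fails a criterion that a subject with one active joint and a full set of evaluable joints meets. Replaced joints are left out at every visit, so for these subjects the effect recurs throughout the study.

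MDA at Week 16 is a key secondary endpoint, and VLDA is among the other secondary endpoints. Their reported rates could partly reflect old surgery, or a joint that the assessor could not score. Two programmers could also report different rates from the same data if one rounds and the other follows the formula literally.

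**Working it through.** The plan states no figure on this point, so there is none to reproduce. The inputs are the SAP 6.2.1.2.1 formula, the ≤ 1 cut-offs and 5-of-7 rule in SAP 6.3.1.5, and the 7-of-7 rule in SAP 6.4.1.3.

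**Step 1: one active joint, m unevaluable joints in that count.** Prorated value = 1 ÷ (N − m) × N.

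| m | TJC68 | SJC66 | ≤ 1? |
|---|---|---|---|
| 0 | 68/68 = 1.000 | 66/66 = 1.000 | met |
| 1 | 68/67 = 1.0149 | 66/65 = 1.0154 | failed |
| 4 | 68/64 = 1.0625 | 66/62 = 1.0645 | failed |
| half of N | 68/34 = 2 | 66/33 = 2 | failed |

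For any m ≥ 1 the value exceeds 1, so only a count of zero passes. Proration never lowers a count, so no subject gains a criterion that the observed count would fail.

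**Step 2: which count is affected.** Protocol Appendix 24 assesses hips for tenderness only. An unevaluable hip moves TJC68 to 68/67 but leaves SJC66 at 66/66. A knee belongs to both counts.

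**Step 3: effect on the endpoints.**

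- VLDA: one failed criterion leaves at most 6 of 7, so VLDA is impossible.
- MDA, one joint criterion lost: subjects with 7 or 6 criteria on observed counts keep 6 or 5 and remain MDA. Those with exactly 5 drop to 4 and lose it.
- MDA, both joint criteria lost: a subject with 7 keeps 5 and remains MDA. Those with 6 or 5 drop to 4 or 3 and lose it.

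Example: one replaced knee, one tender joint, one swollen joint, PGADA 25 (cut-off 20), and the skin, pain, HAQ-DI and enthesitis criteria met. On observed counts this is 6 of 7, which is MDA. Under the SAP it is 4 of 7, which is not. If the replaced joint were a hip, only the tender criterion would fail: 5 of 7, still MDA.

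**Step 4: weight of one subject.** SAP 1.3 reports 67 enrolled. Assuming that the 2:2:1:2 ratio held, a filgotinib or placebo arm has 67 × 2/7 = 19.1 subjects, and one reclassified subject moves its rate by 1/19 = 5.3 percentage points. SAP 6.3.2 analyses MDA on observed cases, so the denominator is the number with a determinable Week 16 result. The documents do not give that number. If it is below 19, each subject weighs more.

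**Step 5: effect of rounding.** One active joint rounds to 1 while N/(N − m) < 1.5:

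- TJC68: 68/46 = 1.478 rounds to 1 and 68/45 = 1.511 rounds to 2, so m ≤ 22 passes.
- SJC66: 66/45 = 1.467 rounds to 1, and 66/44 = 1.5 rounds to 2 with halves rounded up, so m ≤ 21 passes.

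Two active joints give at least 2 and still fail.

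**The case against.** The best defence is that failing the criterion is deliberately conservative. Proration exists because an unassessed joint might be active, and one active joint plus an unknown is not established as at most one. For a joint that could not be scored at a single visit, that has some force. It does not explain failing a subject by 0.015 because of a joint permanently replaced and removed from evaluation. Nor does it explain why one unassessed joint tightens the limit to zero just as 22 would.

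A second defence is that the SAP never forbids rounding, so the point rests on silence. That is so. But SAP 6.4.1.5 does state rounding for the physician's psoriasis score, and the literal reading for joint counts is no rounding.

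Third, the protocol gives no component thresholds for MDA, so no document makes the observed count the true one. This stands, and the comparison here is only with the observed count.

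Fourth, the stakes are modest. The trial stopped at 67 of about 854 planned subjects and p-values are nominal (SAP 3.4). SAP 6.5 allows the p-value for a key secondary binary endpoint such as MDA to be dropped, and SAP 6.4.2 gives VLDA only rates and confidence intervals. By-subject listings of endpoints and components would let affected subjects be found. All of this stands and limits the importance of the point, but it does not remove the inconsistency.

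**Conclusion.** The point holds. Under the SAP as written, a subject with exactly one tender (or swollen) joint and at least one unevaluable joint in that same count scores at least 1.015 and fails the joint criterion. VLDA is then ruled out. MDA is lost only when the failed criterion or criteria bring the total below 5 of 7. Relative to the observed count, the error can only lower response rates. This assumes that the formula is programmed literally.

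A reader might infer more, but the documents do not support it:

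- **That every such subject loses MDA.** The 5-of-7 rule protects those with enough other criteria met.
- **That any unevaluable joint affects both counts.** A hip does not enter SJC66.
- **That the contrast with placebo is diluted.** A residual count of one may be more common where treatment works, but nothing in the documents shows it.
- **That the endpoint moves by a known amount.** The number of subjects affected is not given and could be zero. The 5.3 points per subject rests on about 19 analysed per arm.
- **That the primary analysis is affected.** ACR20 uses percent improvement and has no ≤ 1 cut-off.

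**What to change.** Add one sentence to SAP 6.3.1.5 and 6.4.1.3:

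> For the MDA and VLDA criteria, the TJC68 and SJC66 cut-offs of ≤ 1 are applied to the prorated count rounded to the nearest integer, with halves rounded up.

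Keep the unrounded prorated count for ACR, DAPSA, PASDAS and DAS28(CRP). The SAP is already signed, and its Section 1 provides for later changes to be documented in the CSR, so record this one there.

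The cost is one sentence and one line of code. The downside is that a subject with one active joint and up to 22 (TJC68) or 21 (SJC66) unassessed joints can meet the criterion. One active joint among only half the joints still fails.
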